Based on the experience of the 24 hour audit of Emergency Departments in England, we have assumed that we will be able to recruit at least 50% of eligible ED attendees. We anticipate that the four sites will result in 940 recruits per week. Recruiting over three weeks pre- and post-intervention – giving a total sample size of 5640 – would mean that we would be highly powered (>80%) to detect a decrease in the proportion of alcohol-related attendances from 30% to 25% with 95% significance. We have used a base rate of 30% informed by the 24 hour audit of EDs in England and assumed a 5% decrease would be of public health importance and may be expected based on current evidence. For subgroup analyses, we would have good power (>80%) to detect an effect size of 0.23 on the FAST score among those from the most deprived quintile (estimated to be 25% of attendances) and an effect size of 0.27 among those aged 18-24 (estimated to be 15% of attendances. Two separate follow-up times are required to determine if intervention effects vary over time.

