3.7 Data Collection

Each wave will collect data over three weeks, ideally with one wave of data collection prior to the implementation of MUP and two post-implementation waves (after six months and 12 months). To maximise collection of both alcohol-related attendances and hazardous drinkers, data collection will occur from 2000 to 0400 on Thursday to Sunday (i.e. 32 hours per week during this time period) and 0900-1700 on Monday to Wednesday (i.e. 24 hours per week during this time period). If deemed necessary by local sites, different 8 hour timeslots will be considered, to meet local attendance patterns. As noted above, periods of the year when alcohol consumption is atypical will be avoided.

Patients will be approached by research staff to seek permission to complete a short face-to-face interview. The reasons for exclusion will be recorded electronically on the iPad along with 5 year age group and sex. Excluded patients will not be assigned a study ID and so will be completely anonymous.

All suitable patients will be approached, their eligibility confirmed, and, if eligible, informed consent will be sought and a face-to-face interview administered, based on a previously used patient questionnaire [36]. Research nurses will be responsible for obtaining written informed consent, completing the data linkage form if consent has been obtained -and then proceeding to conduct the face-to-face survey. These will all be electronic documents contained on an iPAD.

The face-to-face survey will collect information on socio-demographic details, problematic alcohol use (FAST Alcohol Screening Test), alcohol consumption in the last 24 hours, self-assessment of whether alcohol contributed to the attendance and self-report of whether the patient has been a victim of violence. Research nurses will input the information into the standardised electronic form which will include a number of options to assist with timely completion. Paper versions of the survey, and consent and linkage forms are enclosed (ED Survey v2.5). The Interview Schedule for Pilot Phase v2.5 and Qualitative Interview for Pilot Phase will be on paper only. Back up paper copies of all electronic documents will be available in case of iPad failure. An ED attendance database will be maintained for all attendances during data collection periods to allow monitoring of patient recruitment.

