Research staff will retrieve additional data on participants from patient records, either during data collection sessions (if time allows), or at a later time. The following information will be sought from the clinical records:

- demographic characteristics (date of birth, sex, postcode),
- attendance details (time, triage category),
- discharge status
- diagnoses at discharge (coded by ICD10 categories) and all relevant data relating to reason for admission and diagnosis (whether ICD10 or another coding system or free text).

We will calculate the consent rate among those eligible. However we need to assess the representativeness of the interviewees and attendees in the study timeslots, and the certainty of our estimates of the proportion of attendances that are alcohol-related. To make this possible, we propose to request from hospital records anonymised information on all attendees over the three week data collection periods for each wave. We wish to ask for 5 year age groups, sex, reason for attendance, and other relevant data for diagnosis (whether ICD10 or another coding system or free text). We will request that attendees within the timeslots for the study are flagged, so that we can calculate a true recruitment rate for those interviewed and for whom we have reasons for exclusion.

Data collection will be conducted by Clinical Research Facilities (CRFs), on behalf of the study team. Each CRF will be responsible for ensuring line management of their staff, as per their usual operating procedures. The research nurses responsible for data collection will have received training, with training available for additional research nurses (to allow for rota gaps to be filled, in the event of illness etc.). It is recommended that any data collection session should include at least one more experienced research nurse, so that more junior research nurses feel adequately supported. Research nurses will be able to contact a member of the study team throughout data collection periods in the event of an emergency.

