3.8 Data Analysis

Primary outcome

The primary outcome will be changes in absolute numbers of alcohol-related attendances as defined by any one of:

- patient self-reports attendance is alcohol-related
- patient reports alcohol consumption in past 24 hours of ≥8units in men or ≥6 units in women
- patient not approached because too intoxicated with alcohol

Secondary outcomes

Secondary outcomes will be changes in:

- absolute number of alcohol-related attendances by age/sex/deprivation
- problematic alcohol use (as defined by the Fast Alcohol Screening Test (FAST))
- mean FAST score
- prevalence of binge drinking in the past week
- reason for attendance (coded by ICD10)

After the first post-intervention wave, we will test for differences in the outcomes between the intervention and comparison groups using a fixed-effects regression model, with individuals nested within EDs, before and after adjustment for relevant covariates including baseline levels of alcohol-related attendance, demography, triage category etc. We will also attempt to determine the nature of the effect more precisely in terms of whether a dose-response effect according to the time since MUP was implemented (through a test of the significance of an interaction between time and intervention). We will test for interactions of the intervention with defined important covariates (including age, gender, deprivation quintile, disease diagnostic categories) to investigate the possibility of differential intervention effects and will subsequently stratify the analyses if indicated.

4. Research Governance and Regulatory Issues

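### The primary outcome adds fully logged intoxicated exclusions to criteria seen only in interviewees, with no scaling, so the recorded number moves with recruitment

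*Protocol*

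**What the plan says.** Protocol 3.8 (Primary outcome) states: "The primary outcome will be changes in absolute numbers of alcohol-related attendances as defined by any one of" three criteria. The first two are "patient self-reports attendance is alcohol-related" and "patient reports alcohol consumption in past 24 hours of ≥8units in men or ≥6 units in women"; both need an interview. The third is "patient not approached because too intoxicated with alcohol", which by definition concerns people who were not interviewed.

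The sources differ in reach. For exclusions, section 3.7 says: "The reasons for exclusion will be recorded electronically on the iPad along with 5 year age group and sex". These records are anonymous and need no consent. For interviews, section 3.3 says: "we have assumed that we will be able to recruit at least 50% of eligible ED attendees".

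The scale is not constant across the document. The outcome in 3.8 is a number, but the power statement in 3.3 is about a share: the study should "detect a decrease in the proportion of alcohol-related attendances from 30% to 25% with 95% significance". The denominator of that share is not defined.

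Sections 3.3 and 3.7 also request anonymised records of all attendees in each wave, with those in the study timeslots flagged, "so that we can calculate a true recruitment rate for those interviewed and for whom we have reasons for exclusion". The stated purpose is to judge representativeness and the certainty of the estimated proportion. The analysis paragraph of 3.8 names a fixed-effects regression and covariates, but no weight, scaling or recruitment offset.

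**The concern.** Section 3.1 describes an audit of all alcohol-related attendances in the departments. What 3.8 counts is a mixture: nearly all of one kind of case, if logging works as planned, and about half of the other two. The half is not a constant of nature. It depends on staffing, crowding and patients' willingness, and can differ by department and wave.

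A change in recruitment between waves therefore changes the recorded outcome when nothing has changed in the population. The effect is read from Scotland against England. If recruitment shifts by the same amount in both, most of the artefact cancels. If it shifts in one country only, the artefact enters the estimated policy effect directly, and its sign depends on whether a count or a share is analysed.

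**Working it through.** **The plan's own figures.** 235 per site per week × 4 sites × 3 weeks = 2820 per wave; 940 × 3 × 2 = 5640 before and after. For 30% v 25% with 2820 v 2820, two-sided 5% (sidedness is not stated), power is 98.8%. The claim of more than 80% is met, so sample size is not the issue here.

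**Inputs.**
- True share of alcohol-related attendances: 30%, falling to 25% (3.3).
- r, recruitment fraction: 0.5 (3.3, a planning minimum), with 0.4 and 0.6 as variations.
- g, share of attendances excluded as too intoxicated: not in the protocol. Assumed 5%, with a range of 1% to 10%.
- a = true share − g: alcohol-related cases detectable only by interview.
- Simplifications: all intoxicated exclusions are logged, non-response is unrelated to alcohol, and other exclusions are ignored.

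**Formulas.**
- Recorded count per 1000 attendances = 1000 × (g + r·a)
- Share of recorded patients (interviewees plus intoxicated exclusions) = (g + r·a) / (g + r·(1 − g))
- Weighted count per 1000 = 1000 × (g + (r·a)/r) = 1000 × (g + a)

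**No true change, g = 5%, a = 25%.**
- r = 0.5: count 50 + 125 = 175; share 0.175/0.525 = 33.3%.
- r = 0.4: count 50 + 100 = 150 (−14.3%); share 0.150/0.430 = 34.9% (+1.6 points).
- Weighted: 50 + 125/0.5 = 300 and 50 + 100/0.4 = 300, the true value both times.

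**Planned true effect, r held at 0.5.** The share falls from 30% to 25% and g falls in proportion, from 5% to 4.17%. The count goes from 175 to 41.7 + 0.5 × 208.3 = 145.8 (−16.7%).

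**Masking.** With the same true fall but r rising from 0.5 to 0.6, the count goes from 175 to 41.7 + 0.6 × 208.3 = 166.7, only −4.8%.

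**Range of g, true share fixed at 30%, r from 0.5 to 0.4.**

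| g | Count per 1000 | Change | Share of recorded patients | Change (points) |
|---|---|---|---|---|
| 1% | 155 to 126 | −18.7% | 30.7% to 31.0% | +0.3 |
| 2% | 160 to 132 | −17.5% | 31.4% to 32.0% | +0.7 |
| 5% | 175 to 150 | −14.3% | 33.3% to 34.9% | +1.6 |
| 8% | 190 to 168 | −11.6% | 35.2% to 37.5% | +2.3 |
| 10% | 200 to 180 | −10.0% | 36.4% to 39.1% | +2.8 |

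The count is sensitive at every g. The share is nearly stable when g is small.

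**The case against.** The strongest reply is that the protocol is silent on weighting and does not reject it. Non-response weights usually belong in a statistical analysis plan, which is not shown. Section 3.1 makes high response and representativeness central, and the data needed for a correction are being requested. A reader might infer that the investigators have chosen an unweighted analysis; the protocol does not say so. What stands against the reply is that the outcome itself is fixed in 3.8 as a raw sum over sources with different reach, and the extract and recruitment rate are given a descriptive purpose only. Followed as written, the result depends on recruitment.

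A reader might also infer that the alcohol-related share is overstated. The protocol does not support that as a general statement. The primary outcome is a number, and the raw number is too low: 175 against a true 300 per 1000 at g = 5% and r = 0.5. Overstatement of a share arises if the denominator is recorded patients (33.3%) or interviewees alone (36.8%). With all attendances as denominator, the share is understated (17.5%). The protocol names none of these.

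Three further points are fair. The value of g is an assumption. Complete logging of exclusions is implied, not guaranteed. A recruitment change common to both countries largely cancels, so the single-series shifts above carry over in full only when the other country's recruitment stays put.

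**Conclusion.** The point holds in this form: the primary outcome is an absolute number that pools criteria with different capture fractions, no scaling is stated, and so both the number and any share built on recorded patients move with recruitment. A change that differs between Scottish and English departments would appear as a policy effect.

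On the count, a 10-point fall in recruitment in one country (50% to 40%) produces −14% at g = 5%, and −10% to −19% over g of 1% to 10%, against −17% for the effect the study is planned to find. On a share of recorded patients it produces +0.3 to +2.8 points, in the opposite direction, against a 5-point target. These sizes rest on the assumed g, a true share of 30%, complete logging and non-response unrelated to alcohol. The dependence on recruitment follows from the outcome definition, provided the interview-only criteria are incompletely captured. It should be settled before the wave comparison; it does not show that the study will be biased, because that requires recruitment to diverge.

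**What to change.** In 3.8:

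1. State the denominator: all attendances within the study timeslots.
2. Estimate alcohol-related attendances as patients meeting the third criterion at weight 1, plus interviewees weighted by the inverse of the recruitment fraction among eligible attendees in the same department and wave. Split by sex and broad age band where numbers allow.
3. Split by night and day only if the extract identifies the slot; attendance time is listed in 3.7 for participants, not for the anonymised extract. Fine cells would be sparse: 235 × 3 = 705 interviews per department and wave, over 2 slot types × 2 sexes × about 15 five-year bands (assumed), gives about 12 per cell.
4. Treat patients excluded for other reasons (too unwell, admitted, left the department and so on) as a separate stratum, with a stated assumption and a sensitivity analysis. Weighting interviewees up to them would silently give them the interviewees' alcohol rate.
5. Use the weighted number, and the proportion of timeslot attendances, in the primary comparison. Show the unweighted result as a sensitivity analysis and report recruitment by department and wave.

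The cost is mainly analysis work, since the exclusion log and flagged extract are already planned. The weights lose some precision (not quantified here) and assume that non-response is unrelated to alcohol within cells. They remove the artefact of changing recruitment, not every form of selection.

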3.3 Participant Selection

The target population for the study is all patients over 16 years age who attend EDs to receive acute treatment for a health condition.

The exclusion criteria for the sample are used to decide whether to approach patients and having approached whether the patient is eligible:

Deemed clinically inappropriate to be approached.

- 'patient too unwell',
- · too distressed,
- grossly intoxicated (alcohol),
- grossly intoxicated (drugs)
- Cognitive impairment
- · Police in attendance,
- Clear language barrier, and no interpreter available
- · Patient already participating,
- routine follow up that has been instigated by ED staff,
- Patient left dept
- Patient admitted,
- staff safety issue,
- End of shift,
- dead on arrival,
- other.

For those who are approached, the inclusion criteria are:

- >=age16
- able to speak English and no interpreter available.
- Is a new ED presentation,
- The patient is conscious
- The patient is physically well enough
- The patient is mentally well enough
- The patient is sober enough (alcohol)
- The patient is sober enough (drugs)
- The patient is still in the department
- The patient is safe for staff to approach

During data collection periods, an ED attendance database will be maintained for all attendances to allow monitoring of patient recruitment. This will help prevent patients being approached on multiple occasions. This attendance database will be destroyed at the end of each recruitment shift. In addition, data on sex, five year age group and diagnoses for all attendees in all the three week waves, with the attendees within the study timeslots flagged, will be requested from hospital records. This is to enable the assessment of the representativeness of our sample and of our estimates of the proportion of alcohol-related attendances.

We intend to obtain a total sample size of at least 2820 participants across all four sites over each three week period of data collection. This equates to 235 participants per week per site of data collection. No target sample size is required for the pilot phases of the study as these phases are intended to help identify potential practical issues involved in conducting the study.

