3.5 Withdrawal and loss to follow up

If the participant loses capacity to consent during the process of data collection, their research data would be withdrawn from the study. As active involvement is relatively short, occurrences of this type of event are expected to be rare.

We will not be planning to re-contact participants after their involvement in the study. This is to ensure that their participation (including attendance at the Emergency Department) in the study can be kept confidential. However, we plan to make a plain language version of the study results available on the study website. A link to the study website will be included on the participant information leaflet and participants will be informed that results will be available from that source. In addition, we plan to work extensively to disseminate the results of the study to the general public through the mass media.

For participants who have provided consent for data linkage, they will have the opportunity to withdraw their consent by contacting the study team. Contact details and information on this process will be included within the Participant Information Leaflet.

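### The third component of the primary outcome counts intoxicated patients only if they were not approached, although eligibility, including sobriety, is also judged after approach

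*Protocol*

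**What the plan says.** Section 3.8 of the protocol opens the definition with "The primary outcome will be changes in absolute numbers of alcohol-related attendances as defined by any one of" three alternatives:

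- the patient's own statement that alcohol played a part in coming to the ED
- a stated intake over the previous day at or above a threshold in units, set separately for each sex
- "patient not approached because too intoxicated with alcohol"

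The first two need the patient's own answers. The third does not, but it is limited to patients who were not approached.

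Section 3.3 describes two uses of its exclusion list: "The exclusion criteria for the sample are used to decide whether to approach patients and having approached whether the patient is eligible". That list contains "grossly intoxicated (alcohol". A second list, for patients who have been approached, contains "The patient is sober enough (alcohol". Section 3.7 gives the order of events: approach, confirmation of eligibility, consent, interview. It also has exclusion reasons entered on the iPad with sex and five-year age group, and gives excluded patients no study ID.

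**The concern.** The third component evidently exists so that patients too drunk to be interviewed still count as alcohol-related. As written it covers only those screened out before approach. The same patient is a case if the nurse judges sobriety from a distance, and not a case if the nurse first starts a conversation and then reaches the same judgement.

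The two lists use different words for the threshold, so a patient can pass the first screen and fail the second. Section 3.6 has staff approach everyone not considered inappropriate, so borderline patients will reach the second screen. Section 3.7 places sessions in the late evening and night from Thursday to Sunday to capture alcohol-related attendances, which makes such patients likely.

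What is at stake is comparability. The outcome is a change in counts, compared between Scottish and English hospitals. If staff at some sites move the sobriety judgement to a later stage between waves, the count falls there with no change in attendances. In Scotland that would look like a benefit of minimum unit pricing. A move to an earlier stage would hide one.

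**Working it through.** **Step 1: trace each path against the three components.**

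| Path | Interviewed? | Components 1 and 2 | Component 3 | Counted? |
|---|---|---|---|---|
| Screened out before approach as too intoxicated | No | Cannot be met | Met | Yes |
| Approached, sober enough, consents | Yes | Met if reported | Not applicable | Yes, if reported |
| Approached, then found too intoxicated | No | Cannot be met | Not met, because approached | **No** |

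No section of the protocol restores the third group to the count.

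**Step 2: reproduce the plan's own figures.** Section 3.3 gives 235 participants per site per week: 235 × 4 = 940 per week, 940 × 3 = 2820 per wave, 2820 × 2 = 5640. Section 3.4's preceding text on sample size (end of 3.3) states power above 80% for a fall from 30% to 25%. With two-sided alpha 0.05 and n per group,

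power = Φ{[Δ − 1.96·√(2p̄(1−p̄)/n)] / √([p₁(1−p₁) + p₂(1−p₂)]/n)}, with p₁ = 0.30, p₂ = 0.25, p̄ = 0.275, Δ = 0.05.

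- n = 2820: (0.05 − 1.96 × 0.01189)/0.01187 = 2.25, power 98.8%.
- n = 1410 (two hospitals per wave): (0.05 − 1.96 × 0.01682)/0.01679 = 1.01, power 84.5%.

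Both agree with the stated figure.

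**Step 3: a constant gap.** Let a share q of alcohol-related cases take the uncounted path in every wave. The counted proportions are 0.30(1−q) and 0.25(1−q), and n is 2820 per wave. The protocol gives no value for q, so the range is assumed.

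| q | Counted before | Counted after | Visible fall (points) | Power |
|---|---|---|---|---|
| 1% | 29.7% | 24.75% | 4.95 | 98.7% |
| 2% | 29.4% | 24.5% | 4.9 | 98.6% |
| 5% | 28.5% | 23.75% | 4.75 | 98.2% |
| 10% | 27.0% | 22.5% | 4.5 | 97.5% |

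**Step 4: a shift in path with no true change.** Let a share s of cases at a 30% base rate move from being screened out before approach to being excluded after it. The false change is 30 × s points. At 30%, 2820 attendances contain 846 cases. The planned fall is 846 − 705 = 141 cases.

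| s | False change (points) | Share of the 5-point target | Cases per 2820 |
|---|---|---|---|
| 1% | 0.3 | 6% | 8.5 |
| 2% | 0.6 | 12% | 16.9 |
| 5% | 1.5 | 30% | 42.3 |
| 10% | 3.0 | 60% | 84.6 |

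The percentage-point scale is used because the sample size is stated on it, and applying it to 2820 only sets the scale. If the shift occurs at one of a country's two equally sized hospitals, that country's false change is half: 0.15 to 1.5 points. If it occurs equally in both countries, it cancels in the comparison between them.

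**The case against.** The best defence is that this is loose wording in one bullet. The exclusion list, with its intoxication item, applies at both stages. Reasons are recorded on the iPad, and section 4.1 says eligibility screening is done there. An analyst could count these patients with a coding rule, and a statistical analysis plan may contain one. Pre-approach screening, with senior ED staff consulted in doubt (sections 3.4 and 3.6), should leave few patients to be found intoxicated later. Training, a pilot at all four sites and the coordinator's duty to keep processes consistent (sections 3.6 and 3.7) all work against drift.

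Much of this stands. It limits the likely size and shows that the remedy is simple. It does not remove the point: the definition is stated in the protocol, and following it consistently still omits the group.

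Some stronger readings are tempting but unsupported:

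- **The cases are lost for good.** A reader might infer this, but the recorded reason should allow them to be recovered. They are missing from the count as defined, not from the data.
- **Intoxicated patients logged under another reason, such as police presence, staff safety or having left, are also missed.** This presumes a form that accepts only one reason. The exclusion screen is not in the document.
- **The withdrawal rule in section 3.5 is a further leak.** It reads "If the participant loses capacity to consent during the process of data collection, their research data would be withdrawn from the study". That concerns people already taking part, not patients excluded at screening, and the protocol expects it to be rare.

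**Conclusion.** The point holds as a mismatch between the wording of the primary outcome and the two-stage eligibility process. Its severity is minor to moderate. A constant gap shrinks the visible fall in proportion and barely affects power. A difference between sites or waves in the stage at which sobriety is judged would bias the change in counts, by 0.3 to 3.0 points over the assumed range.

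That range is an illustration. It assumes a 30% base rate, no true change, and 1% to 10% of cases switching path at all sites being compared. The protocol gives no frequency for this path, so a reader should not conclude that a bias of any particular size is expected, or that the primary result would be invalid without the change.

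**What to change.** Reword the third component in section 3.8 to: *patient excluded, before or after approach, because too intoxicated with alcohol*. Have the iPad record the stage of exclusion (before or after approach) alongside the reason, and apply both identically at all sites and in all waves. The rewording makes the count independent of the stage. Recording the stage lets the team see whether practice moved between sites or waves.

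Keep the words about being too intoxicated. A broader rule that counted anyone not interviewed and noted as having drunk would drop that threshold. It would also bring in patients who refused or left, and ask staff to judge people they may not have seen.

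The cost is one sentence in the protocol and one small form item, with no extra staff.

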3.1 Study Design

This research is a natural experiment study of the impact of introducing MUP in Scotland. The methods involve a repeated cross-sectional audit of all alcohol-related attendances at EDs in two Scottish hospitals and two North England geographical control hospitals at three time points. On each occasion, data collection will involve a face-to-face survey administered by research nurses to ED patients over selected times during a three week time period. All study documents with the exception of the patient information sheet and consent form will be

electronic and held on an iPad. Back up paper copies will be available in case of iPad failure. The study methods and tools are based on previous studies that have been used to quantify the national prevalence of alcohol-related attendances in Emergency Departments in England [36] and by the experience of the Scottish Emergency Department Alcohol Audit, carried out across 15-20 hospitals throughout mainland Scotland between October 2005 and June 2007 [37]. Prior to formal data collection, the processes for collecting data will be piloted – initially within Glasgow only, followed by pilot data collection at all four sites.

The study has been designed to be robust to potential delays in the timing of the intervention. Since the implementation of MUP is not under the control of the investigators, it is possible that there may be delays in the timing of the intervention. Baseline data collection will occur as soon as is practically possible. The 2nd and 3rd waves of data collection will take place six and 12 months post implementation. If implementation of MUP occurs more than 12 months after baseline the 2nd wave will be conducted shortly before implementation to act as a 2nd baseline. The 3rd wave will remain as close to a 12 month follow-up as feasible. If this occurs, it will not be possible to investigate whether the intervention effect varies over time (RO5). In general, investigators will attempt to avoid conducting data collection during months that are expected to be atypical in terms of alcohol consumption (i.e. Dec-Jan and Jun-Aug). Furthermore, we will attempt to collect data for one follow-up wave at the same time of year as the baseline data, to control for seasonal variation in consumption.

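### The named model and the power calculation allow for no ED-by-wave or random shift variation; with model-based standard errors, any such variation makes the interval for the MUP effect too narrow

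*Protocol*

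**What the plan says.** Section 3.8 (Data Analysis) tests for differences between intervention and comparison groups after the first post-intervention wave, "using a fixed-effects regression model, with individuals nested within EDs", before and after covariate adjustment. No term for shift or for ED-by-wave is named, and no method for the standard errors is given. The primary outcome in the same section is a change in a count of alcohol-related attendances. That count includes patients who were not approached because they were too drunk.

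Section 3.1 sets the design: "two Scottish hospitals and two North England geographical control hospitals at three time points", with new patients in each wave.

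Section 3.7 samples in 8-hour slots: "data collection will occur from 2000 to 0400 on Thursday to Sunday", plus Monday to Wednesday days. Sites may use other 8-hour slots.

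Section 3.3 gives the size. "This equates to 235 participants per week per site of data collection", and one wave before and one after MUP are combined, "giving a total sample size of 5640". On that basis it says "we would be highly powered (>80%) to detect a decrease in the proportion of alcohol-related attendances from 30% to 25" per cent, "with 95% significance". No intraclass correlation or design effect appears.

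**The concern.** The policy contrast is the change in two Scottish EDs minus the change in two English EDs. A fixed effect for ED takes out whatever is constant about that ED. A shift in the level of one ED between waves stays in, and with two EDs per country half of it passes directly into the country's change. Random variation between shifts adds a further layer, because patients arrive in blocks of about 34 who share the same night, staff and local events.

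The protocol itself shows how ED-by-wave changes could arise. Research staff judge who is too intoxicated to approach, and that judgement counts towards the primary outcome. Separate Clinical Research Facilities collect the data and fill rota gaps with other nurses. Section 3.7 makes a coordinator responsible for keeping procedures consistent between sites and over time.

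If this variation is left out of the standard error, a chance change at one or two hospitals can be reported as a policy effect, or as firm evidence of none. Sections 2.2 and 6.3 say the results feed the report to the Scottish Parliament and the decision on whether MUP continues.

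**Working it through.** **Inputs from the protocol.** 235 recruits per site per week; 4 EDs, 2 per country; 3 weeks per wave; 7 slots per week (4 nights, 3 days); 30% base rate; 5% level, taken as two-sided because the sidedness is not stated.

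**Inputs assumed.** ED-by-wave SD of 1 to 2 percentage points; residual shift ICC of 0.005 to 0.02. Neither is in the protocol.

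**1. The plan's own figure.** 235 × 4 × 3 = 2820 per wave, and 2 × 2820 = 5640. Comparing 30% with 25% in 2820 v 2820 independent patients gives 98.8% power; Scotland alone, 1410 v 1410, gives 84.5%. The stated >80% is reproduced as a before/after comparison of independent patients.

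**2. ED-by-wave variation.**
- Sampling variance of the difference in changes: 4 × 0.30 × 0.70 / 1410 = 0.000596.
- Each country-wave mean averages two EDs, so an ED-by-wave SD of s adds 4 × s²/2 = 2s².
- True error = 2Φ(−1.96/√R), where R is the total variance over the sampling variance.
- s = 0.01: R = (0.000596 + 0.0002)/0.000596 = 1.34; error 9.0%.
- s = 0.02: R = (0.000596 + 0.0008)/0.000596 = 2.34; error 20.0%.

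**3. Random shift variation.**
- Recruits per shift: 235/7 = 33.6. Shifts: 7 × 3 = 21 per ED-wave, 84 per wave.
- Design effect = 1 + 32.6 × ICC; true error = 2Φ(−1.96/√(design effect)).

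| Assumed ICC | Shift SD, √(ICC × 0.21) | Design effect | True error |
|---|---|---|---|
| 0.005 | 3.2 points | 1.16 | 6.9% |
| 0.01 | 4.6 points | 1.33 | 8.9% |
| 0.02 | 6.5 points | 1.65 | 12.7% |

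**4. Simulation.** No true effect, 20,000 runs per scenario, 34 patients × 21 shifts per ED-wave, linear model with ED fixed effects, country-by-wave terms and model-based errors.

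| Scenario | Rejections at nominal 5% |
|---|---|
| No extra variation | 4.8% |
| ED-by-wave SD 1 / 2 points | 8.8% / 20.1% |
| Random shift SD 3 / 5 / 8 points | 7.0% / 9.8% / 17.0% |
| Fixed night/day gap (40% v 17%), same timetable in both waves | 4.3% |

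A t-test on the four ED-level changes (2 df) stayed between 4.7% and 5.2% throughout.

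**5. Effect on the stated power.** With 705 patients per ED-wave, an ICC of 0.0005 (SD about 1.0 point) gives a design effect of 1 + 704 × 0.0005 = 1.35, and an ICC of 0.002 (about 2.0 points) gives 2.41. Dividing 2820 by these reduces the 98.8% to 95% and 77%.

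**The case against.** A reader might infer that the plan treats patients as independent within ED and that its 5% level therefore fails. The protocol does not support that. It names no standard-error method; robust or bootstrap errors would be compatible with its sentence, and the variance estimator is commonly left to the SAP, which is not at hand. It also gives no variance, and without extra variation the test holds its level. The claim has to be conditional and its size given as a range. What the protocol does fix is the grouping structure of the model and a sample size without a design effect.

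A reader might also infer that mixing nights and days inflates the error. It does not if the timetable is repeated in each wave, because the gap cancels. Only random shift-to-shift variation counts, and planned covariate adjustment may absorb some of it. The freedom to choose other slots matters only if a site's slots differ between waves.

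Two further objections stand. The figures are for a proportion among recruits, while the primary outcome is a count, where the same variation would appear as over-dispersion; the percentages do not transfer directly. And clustering on shift leaves the ED-by-wave part, potentially the larger one, outside the interval. That is largely a limit of a four-hospital natural experiment, and section 3.1 already concedes that confounding is possible. It still needs stating where the interval is defined.

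**Conclusion.** The point holds in conditional form. The named model has ED as its only level, and neither it nor the power calculation allows for ED-by-wave or random shift variation. If model-based errors are used and such variation exists, the interval is too narrow. Under the assumed ranges, on the proportion scale, a nominal 5% test has a true error of about 9% to 20% from the ED-by-wave part, and about 7% to 13% from the shift part, each taken alone. The ED-by-wave part is the more serious, because a standard deviation of only 1 point nearly doubles the error and shift clustering does not remove it. The protocol does not show that the 5% level is in fact lost.

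**What to change.** In section 3.8:

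- Cluster the standard errors on ED-shift (84 shifts per wave). For the count outcome, analyse ED-shift counts with a variance robust to over-dispersion. Clustering on ED instead is not a safe substitute, since robust errors are unreliable with four clusters.
- Pre-specify a sensitivity analysis on the ED-by-wave values: a comparison of the four ED-level changes on 2 df, with all four changes shown.
- State that the primary interval does not cover ED-by-wave variation, and that a significant result without support from the ED-level analysis will not be attributed to MUP with full confidence. Say in advance what counts as support.

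In section 3.7, log date and shift for excluded patients, including those too intoxicated. Attendance time is retrieved for participants, but for excluded patients only reason, age group and sex are listed, and section 3.3 has the attendance database destroyed after each shift. Because nights cross midnight, record the date on which the shift began.

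The cost is some wording and code, one extra field on the exclusion form, and wider intervals. The ED-level analysis has low power. Using the sampling variance alone, the standard error is √0.000596 = 2.44 points. The half-width is then about 4.30 × 2.44 = 10.5 points on 2 df, against 1.96 × 2.44 = 4.8 points for the model-based interval. It can qualify the primary result but could seldom confirm a 5-point effect by itself.
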